93. *The Family and Medical Leave Act of 1993: Leave for Treatment of Substance Abuse*. 1993 [cited 2021 September 23]; Available from: <https://www.law.cornell.edu/cfr/text/29/825.119>.

94. Substance Abuse and Mental Health Services Administration. *Plan and Implement a Program*. 2020 [cited 2021 October 14]; Available from: <https://www.samhsa.gov/workplace/toolkit/plan-implement-program>.

95. Substance Abuse and Mental Health Services Administration. *Tip 63: Medications for Opioid Use Disorder*. 2018 2021 [cited 2021 October 13]; Available from: https://store.samhsa.gov/sites/default/files/SAMHSA_Digital_Download/PEP21-02-01-002.pdf.

96. Howard, J., et al., *Medication-Assisted Treatment for Opioid Use Disorder*. Workplace Solutions, 2019.

E. Monthly Health Fund meeting script_followup

Monthly Health Fund follow-up meeting:

Date: _____

Organization: _____

Participant: _____

Notes from past Interview:	
1. Are you in the process of making any changes to your opioid prevention program? If yes please describe (date of adoption,	

implementations strategies, how are you measuring effectiveness of the change, participation rates in programs for workers, adherence to and enforcement of policies, and methods for disseminating programs)
 
a. Have you made any changes to existing opioid prevention programming? If so please explain
	

2. Did you review the guidelines? If yes, what did you find useful and what do you think is missing from the guidelines?
 
a. Did you complete the needs assessment?b. Did you follow the process guide, steps 1, 2, and 3?c. What did you list on your inventory of resources?d. Did you make a plan?	

3. What are challenges or barriers are you encountering in trying to implement your program?
	

G. Data management of Administrative Health Claims and Worker Surveys
Data management of Administrative Health Claims and Worker Surveys

a) Administrative Health Claims

a. Inclusion

- i. Health plan member (as opposed to dependent or retired) at some point during study period (6/1/2019-5/31/2022), per census records
 - 1. Could transition to retired status during study period, but needed to start as member

b. Exclusion

- i. Missing eligibility or termination dates in census records
- ii. Cancer diagnosis
 - 1. Ever received ICD-10 code in medical claims data: C00.x–C26.x, C30.x–C34.x, C37.x–C41.x, C43.x, C45.x–C58.x, C60.x–C76.x, C77.x–C85.x, C88.x, C90.x–C97.x)

c. Initial work

- i. Medical claims (“claims”), pharmacy claims (“fills”), census data was received “piecemeal”
 - 1. By timeframe (i.e, quarterly) and type (plan member, dependent, retired)

- ii. Consolidate files into single datasets for claims, fills, census data and work histories
- iii. Create eligible/valids file—this is the list of members eligible for the study, based on above criteria
- iv. Limit all analysis data (claims, fills) to members in the eligible/valids list
- d. Opioid/claim linkage: The process of linking opioid prescriptions (from pharmacy fills) to diagnoses (from medical claims) involves two main steps: 1) assign opioid fills to claims based on timing and acuity, and 2) assign opioid refills to claims
 - i. Opioid/claim join using timing and acuity
 - 1. Create file of opioid fills from pharmacy fills data, using CDC file ["CDC opioid NDC_oral MME conversion_update_2020.xlsx"] to identify opioids
 - 2. Split opioid claims into two groups based on refill status: initial fills and refills (note this is using refill status indicated by the health fund. Many members have serial initial fills and not refills in these data; those would be in the initial fills file)
 - 3. Assign diagnosis category for each claim, using ICD-10 and procedure codes. Categories include “MSD surgery”, “Acute MSD injury”, “Chronic MSD”, and “Other diagnosis”
 - a. If more than one diagnosis category is present on a single claim, assign claim to the highest acuity (MSD Surgery, then Acute MSD Injury, then Chronic MSD, then Other diagnosis)
 - 4. Join claims with initial fills by member ID (UID)—this generates a many-to-many match
 - 5. Calculate time difference between claim date and fill date
 - a. If fill<before claim, use this information to generate opioid naïvety status for each claim
 - 6. If fill is 0-3 days after claim and the claim diagnosis category is not “Chronic MSD”, assign the opioid to the claim. If more than one claim fits the criteria, assign based on order other diagnoses, then MSD surgeries, lastly acute MSD injuries. If more than one claim is still eligible, use the smallest time difference between claim and fill to assign the fill
 - 7. Among the unlinked opioid fills, if fill is 0-30 days after a chronic MSD claim, assign opioid to that claim. If more than one claim meets the criteria, assign based on time difference (i.e., smallest time difference between claim and fill date)
 - ii. Assign opioid refills to claims
 - 1. Serial prescriptions (most common scenario)
 - a. Start with all opioid first fills (including unlinked and linked with medical claims, using the process above)

- b. Arrange all fills by UID and fill date
 - c. Assign fills to claims that 1) occur after a claim with a linked opioid fill, and 2) opioid fill date is no more than 30 days after previous fill runout date (fill date + days supply)
2. Refills specified in the pharmacy data
 - a. Join opioid refills (from 1b above) with the first fills using prescription identifier ("RXNUM").
 - b. Assign claim information from first fills to linked refills

Variable definitions

- e. Opioid-related variables. These variables were generated using information from the medical claims and pharmacy fill data from the health fund and the CDC opioid file "CDC opioid NDC_oral MME conversion_update_2020.xlsx". The CDC file was merged with health fund pharmacy fill data on NDC
 - i. Medication assisted treatment (MAT): Drug name contained "methadone" or "buprenorphine" in either file or drug description was "ANTIDOTES AND SPECIFIC ANTAGONISTS" in the pharmacy fill file
 1. This strategy picks up buprenorphine, suboxone, zubsolv, naltrexone, methadone, narcan, and vivitrol
 - ii. Opioid: pharmacy class was "opioid" in the CDC file, and the drug was not already identified as MAT (see above)
 - iii. OUD: ever ICD-10 code "T40x" or "F11x" on a medical claim or identified as MAT (see above)
 - iv. Days supply > 7 days: based on "days supply" as provided in fill data
 - v. MME/day: Instructions for calculation are in CDC file. Formula is "strength per unit" * "average quantity per day" * "MME conversion factor"
 - vi. Overlapping Rx: Date opioid fill is within previous days supply (current fill date < previous fill date + days supply)
 1. When the previous prescription is a "short course" (the prescription window is encompassed by prescription before it), the prescription before the short course is used in evaluation
 - vii. Chronic use (>60 days supply in a 90 day window)
 1. For each worker time is divided into 90 day "cycles", starting with the date of the first opioid fill
 2. Days supply is totaled within the 90 day cycle
 3. If the individual had opioid fills later than 90 days after the first fill, a new cycle is started and the process starts over
 4. When workers have multiple opioids filled on the same day, use the longest days supply in calculations
 5. Indicator variable for total days supply in a cycle > 60 for any given cycle
 - viii. Multiple Rx in a single visit: multiple Rx filled on the same day and NPI is the same between fills

- ix. Multiple Rx on same day, different provider: multiple Rx filled on the same day and NPI between Rx different. Could indicate doctor shopping
- x. Misuse: “Overlapping Rx” OR “Multiple Rx on same day, different provider”
- f. Diagnoses. These variables were generated from information in the medical (i.e diagnosis and procedure) claims. Diagnoses are assessed at the claim level, and “rolled up” to the worker (i.e, has worker ever had a diagnosis for X)
 - i. MSD surgery: CPT codes 20005-21010; 21500-22900; 62263-63746; 64400-64999
 - ii. Acute MSD injury: ICD-10 codes ranging S00-T14
 - iii. Chronic MSD: ICD-10 codes M.x, G54-G57
 - iv. Recurring acute injury. Acute MSD injuries that occur across multiple claims are recoded as “recurring injuries”. These are combined with chronic MSD for our purposes
 - 1. ICD-10 codes for acute MSD injuries are identified on a given claim (see above)
 - 2. If the same ICD-10 code occurred on a previous claim more than 30 days before the claim in question, the acute MSD injury is recoded as “recurring injury” on the claim in question and will no longer be counted as an acute MSD injury
 - 3. Using this method, the first occurrence of a given acute MSD injury ICD10 code will be left as “acute MSD injury”
 - v. Other diagnosis: Claims that do not fit into i-iv above are coded as “other Dx”
 - vi. Acuity: claims can have multiple diagnoses associated with them. Acuity is assigned as follows, regardless of other diagnoses associated with the claim: MSD surgery, Acute MSD Injury, recurring injury or chronic MSD, other diagnoses.
 - 1. So if a claim had codes for both MSD surgery and chronic MSD, the acuity is assigned to MSD surgery
- g. Description of the study sample [all data are in “claims eligibility_20230213.docx”, unless otherwise noted]
 - i. Demographics and worker characteristics
 - 1. Gender
 - 2. Age in 2022
 - 3. Plan status (Active, COBRA, etc)
 - 4. Time worker eligible for benefits during study period
 - 5. Gaps in eligibility
 - ii. Plan utilization
 - 1. Proportion of workers with a health claim, pharmacy claim, overlap of these
 - iii. Distribution of diagnoses based on original order of acuity
 - iv. Diagnoses. Number of workers with:
 - 1. MSD surgery
 - 2. Acute MSD injury

3. Chronic MSD or recurring acute injuries
4. Other diagnoses

- v. Opioid utilization. Number of workers with:
 1. At least one opioid fill
 2. Ever days supply > 7
 3. Ever MME/day > 50
 4. Ever MME/day > 90
 5. Overlapping Rx
 6. Chronic use (>60 day supply in 90-day period)
 7. Multiple Rx on the same day, same provider
 8. Multiple Rx on the same day, different providers
 9. Misuse
- vi. OUD
 1. N by source (diagnosis, MAT fill, both)

- h. Medical claim/opioid linked data
 - i. Distribution of opioid fills by diagnosis, as captured on linked claim

- b) Worker Surveys
 - a. Worker surveys will be distributed to all members of each health fund at start of project, to collect a sample of 300 surveys. We will collect another sample of 300 surveys after 6 months.
 - b. We will examine the serial cross sectional data (baseline & 6mos) by comparing sample characteristics.
 - Age, x
 - gender, x
 - race, x
 - hisp, x
 - unionbenefits, x
 - employstatus, x
 - time_construction, x
 - months_construction, x
 - constype;x
 - c. We will examine the items related to each of the three outcomes of interest
 - i. Opioid misuse- A “yes” response to either of the following two items:
 1. Did you use the pain medication more than prescribed, or for a longer period than prescribed? [pnmed_longer]x
 2. Have you used prescription pain medications that were prescribed to someone else? [pnmed_othersrx]x
 - ii. Proportion of workers with lost time- A “yes” response to either of the following two items:

1. Please refer to the last 12 months for the following questions: Did you miss any days of work because of your pain or discomfort? [missday_pn]x
2. In the past 12 months, have you gone to work intoxicated, high, or recovering from the night before? [missday_intox] [*possible reduced productivity]x
- iii. Proportion of workers who are willing to seek help
 - 1) their workplace
 1. If I was struggling with a substance use problem... I would be willing to seek help from my supervisor or someone in human resources [help_sup_hr]x
 2. If I was struggling with a substance use problem... I would be willing to seek help from a professional (MAP or behavioral health) [help_prof]x
 3. If I was struggling with a substance use problem... I would be willing to ask a trusted coworker for help [help_coworker]x
 4. Have you attended Alcoholics or narcotics anonymous (AA/NA) group [aa_na_use]x
 5. Have you met with the specialist? [peer_supp_use]x
 - 2) professional help (employee assistance program or behavioral health)
 6. If benefit is available.... Union sponsored Member assistance program (MAP) [eap]x; Have you used these benefits? Member assistance program (MAP) [eap_use]x
 7. If benefit is available.... Behavioral health (counseling) [behav_health]x; Have you used these benefits? Behavioral health (counseling) [behav_health_use]x

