9.4 STATISTICAL ANALYSES

9.4.1 GENERAL APPROACH

Outcome data is derived from the administrative claims and worker surveys.

Administrative claims will be collected over two periods (06/01/2019-05/31/22) and (06/01/2022-05/31/2023). All three outcomes of interest are primary outcomes. The analysis will examine the group level change of the outcome, adjusting for length of time in each period, to show a reduction in impaired health or behaviors that may be due to implementation of the intervention.

Worker surveys will be collected by member worker surveys from each health fund at two points in time. The baseline, before implementation of the intervention, and at 6-months after start of implementation. All members will be invited to complete a survey. The desired sample is 300 surveys per health fund at each time point. The outcomes are composed of one or more items in the surveys. Group level statistics will be computed as the proportion of members with a positive response to each outcome. The change in proportion by time point may be due to implementation of the intervention.

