9.4.2 ANALYSIS OF THE PRIMARY ENDPOINT(S)

- a) Administrative Claims
 - a. Outcome variables of interest
 - i. Opioid misuse- “Overlapping Rx” OR “Multiple Rx on same day, different provider”
 - ii. Chronic opioid use- more than 60 days supply in a 90 day window
 - iii. Opioid use disorder- ICD-10 T40* (Poisoning by, adverse effect of and underdosing of narcotics and psychodysleptics) &/Or ICD-10 F11* (opioid related disorders) &/or prescribed MAT (Drug name contained “methadone” or “buprenorphine”; picks up buprenorphine, suboxone, zubsolv, naltrexone, methadone, narcan, and vivitrol)
 - b. Compute statistics for baseline period (06/01/2019-05/31/2022) and follow-up (06/01/2022-05/31-2023)

- i. Categorical data will be presented as N (%), continuous data as median (25th, 75th %tile)
- c. Run comparisons between baseline and follow-up time points
 - i. Comparisons involving two categorical variables will be made using Fisher's exact test
 - ii. Comparisons involving a continuous variable and a categorical variable will be made using Wilcoxon Rank Sum test or Kruskal Wallis test

b) Worker Survey

- a. Outcome variable of interest
 - i. Opioid misuse- Participant responded yes to one of the following two questions:
 - 1. Did you use the pain medication more than prescribed, or for a longer period than prescribed? [pnmed_longer]x
 - 2. Have you used prescription pain medications that were prescribed to someone else? [pnmed_othersrx]x
 - b. Compute the change at 6 months post-intervention (change of opioid misusep) of group-level data collected from groups of health

All endpoints are independent outcomes.

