- Neither Agree nor Disagree
- Agree
- Strongly agree

If I was struggling with a substance use problem...

	Yes	No
I would be willing to seek help in human resources		from my supervisor or someone
I would be willing to seek help in behavioral health		from a professional (MAP or
I would be willing to ask a trusted coworker for help		

You have completed the survey. Thank you. Please press submit

C. Administrative Claims_Data Variables

Label	Variable name	database	Description
Patient Identifier	Patient ID	Claims	Unique identifier created by health plan to allow linkage of the datasets (pharmacy and claim data)
Claim date	claimDate	Claims	date of claim
Claim type	claimType	Claims	code for type of claim
Provider identifier	providerSrv ID	Claims	Unique identifier in health plan database for provider
Primary diagnosis (ICD-10)		Claims	primary ICD-10 code
All diagnoses (ICD-10 codes)	allDiagnosis	Claims	ICD-10 codes for the visit
CPT and HPCCS codes	procedureCode	Claims	CPT and HPCCS codes
Claim start date	serviceFrom	Claims	start date of claim episode
Claim end date	serviceThru	Claims	end date of claim episode
Claim episode	Sequence	Claims	number to group rows of data for each single episode
Patient Identifier	Patient ID	Pharmacy	Unique identifier created by health plan to allow linkage of the datasets (pharmacy and claim data)
Pharmacy date of service	Date of Service	Pharmacy	Pharmacy date of service
Pharmacy location identifier	Pharmacy RX No	Pharmacy	Pharmacy location identifier
Drug name	Drug Name	Pharmacy	drug name
Drug type	Drug Type	Pharmacy	drug type
Drug identifier	NDC	Pharmacy	drug identifier
Refill number	Rx Refill Nbr	Pharmacy	number of the refill
Formulary category	Formulary Ind	Pharmacy	single or combination drug
Indication for drugs	Most Common Indication	Pharmacy	category of indication for drugs (i.e. pain/inflammation)
drug for maintenance	Maintenance Drug	Pharmacy	purpose of drug
number of days	Days Supply	Pharmacy	number of days supply
number of tablets	Fill QTY	Pharmacy	number of tablets per drug
Claim correction	Claim count Nbr	Pharmacy	Used to correct misentries in data
Relationship code	Relshp Cde	Pharmacy	relationship of the patient (member, spouse, dependent) to identify possible non-member data in the dataset
Age	Age	Pharmacy	Computed by the health fund, age at time of first claim
Gender	Gender	Pharmacy	sex of patient

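### One Narcan, methadone or buprenorphine fill makes a worker an OUD case with no diagnosis or indication check, and MAT-coded fills no longer count as opioid fills

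*Combined protocol and SAP*

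**What the plan says.** The rules are in the Additional Information item on data management of administrative health claims, variable definitions e.i to e.x.

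- **MAT (e.i).** A fill is MAT if its name contains methadone or buprenorphine in either the fund file or the CDC file, or if the fund's drug description is the antidotes and antagonists class. The appendix adds: "This strategy picks up buprenorphine, suboxone, zubsolv, naltrexone, methadone, narcan, and vivitrol". No diagnosis, indication or formulation condition is attached.
- **Opioid (e.ii).** The pharmacy class must be opioid "in the CDC file, and the drug was not already identified as MAT".
- **OUD (e.iii).** A worker is a case if a T40 or F11 code ever appears "on a medical claim or identified as MAT". One MAT fill is sufficient.
- **Overlap (e.vi).** "Overlapping Rx: Date opioid fill is within previous days supply". This is one of the two arms of misuse.
- **Chronic use (e.vii).** The 90-day cycles start at the first opioid fill.

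Section 9.4.2 also makes MAT a stand-alone route to OUD, but gives only the two-name rule. It nevertheless says that this rule "picks up buprenorphine, suboxone, zubsolv, naltrexone, methadone, narcan, and vivitrol". It lists misuse, chronic use and OUD as the claims outcomes, and section 9.4.1 says "All three outcomes of interest are primary outcomes".

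The claims variable list (Appendix C) requests an indication category for each drug and a patient identifier that links pharmacy to medical claims. Rules e.i to e.iii use neither to decide what a fill was for.

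**The concern.** A drug name or a broad pharmacy class is being used as a diagnosis. It can fail in two ways.

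First, the antidote class brings in Narcan, a rescue product. The guidelines under test encourage naloxone programs, so the intervention could itself raise a component of a primary outcome that it is meant to lower.

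Second, methadone and buprenorphine are also prescribed as analgesics. That is general pharmacological knowledge and is not stated in the documents. For a worker given them for pain, one rule adds a false OUD case and removes the same fills from the overlap and chronic-use calculations.

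At stake are the claims-based levels, the baseline to follow-up comparison, and the rates that section 9.2 says will inform power for a later trial.

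**Working it through.** The plan states no rate or sample-size figure for these outcomes, so there is none to reproduce. The check is of the rules as written, followed by an illustration of size.

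**1. Narcan against the trial's own guidelines.** The guidelines' resource list (14.6) treats Narcan and naloxone as the same drug. The critical incident response section describes naloxone as reversing an overdose. The section on treatment and recovery names three medications for recovery: buprenorphine, naltrexone and methadone. Naloxone is not among them. The employee education strategies (15.1.1) and the critical incident section both promote workplace naloxone programs. Under e.i and e.iii, a worker with one Narcan fill in the pharmacy claims and no F11 or T40 code is an OUD case.

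**2. Methadone or buprenorphine for pain.** Rules e.i to e.iii, e.vi and e.vii were applied to two constructed workers with no F11 or T40 code.

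| Worker | Coding | OUD | Opioid fills | Overlap | Chronic use |
|---|---|---|---|---|---|
| A: three 30-day methadone fills for pain, days 0, 25, 50 | as written | yes | 0 | no | no |
| A | pain fills kept as opioids | no | 3 | yes | yes |
| B: as A, plus 30-day oxycodone fills on days 5, 30, 60 | as written | yes | 3 | yes | yes |
| B | pain fills kept as opioids | no | 6 | yes | yes |

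For A, day 25 falls before day 0 + 30, so there is overlap, and 3 × 30 = 90 days' supply exceeds 60, so use is chronic. Neither is seen once the fills are MAT. B still qualifies through oxycodone. So fills are removed rather than workers. The same-day, different-provider arm of misuse (e.ix) does not say that it is limited to opioid fills, so its behaviour is undetermined.

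**3. Section 9.4.2 against the appendix.** The strings methadone and buprenorphine do not occur in naltrexone, Narcan or Vivitrol. The two-name rule in 9.4.2 therefore cannot pick up these three products. Only the appendix, through the antidote class, has a route to them, so the two texts can give different OUD counts.

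**4. Illustrative size.** Members: 3 × 10,200 = 30,600 (section 9.2). Both rates below are assumptions:
- q, share given methadone or buprenorphine for pain without true OUD and without an F11 or T40 code: 0.02% to 0.2%
- p, true OUD: 0.5% to 2%

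False cases = 30,600 × q: 30,600 × 0.0002 = 6 and 30,600 × 0.002 = 61. True cases = 30,600 × p: 153 to 612. Share of counted cases that are false = q/(p + q):
- smallest: 0.0002/(0.02 + 0.0002) = 1.0%
- largest: 0.002/(0.005 + 0.002) = 28.6%

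For Narcan, suppose the share of workers with a Narcan fill and no other route to OUD rises by d between periods. The OUD proportion then rises by d with no change in disorder. With d = 0.1 percentage points and p = 1%, 1.0% becomes 1.1%, an apparent increase of 0.1/1.0 = 10%. Again d is assumed.

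**The case against.** The strongest case against has five parts.

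- **Outside premise.** The documents describe methadone and buprenorphine only as recovery medications and give no sign of how many members receive them for pain. This stands for the pain arm, whose size is pure assumption. It does not touch the Narcan arm or the mismatch with 9.4.2, which rest on the documents.
- **Mitigation.** The appendix tabulates OUD by source (diagnosis, MAT fill, both), and cancer patients are excluded. The table would expose MAT-only cases, but it does not change the outcome or return fills to the opioid file. The cancer exclusion leaves non-cancer pain.
- **Purpose.** The guidelines encourage cover for MAT. If true MAT fills stayed in the opioid file, successful treatment would look like chronic use. That is a good reason to keep true MAT out, and the fix does so.
- **Change, not level.** Similar error in both periods affects levels more than change. Correct, but similarity cannot be assumed when the guidelines promote naloxone programs, buprenorphine cover and tighter opioid limits.
- **Feasibility.** Section 9.1 disclaims formal testing and section 3 disclaims power. This lowers the urgency, although 9.4.2 still plans Fisher's exact tests between periods.

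A reader might infer more than the text supports. Workers on these drugs do not disappear from misuse and chronic use: those with other opioid fills can still qualify, and the same-day arm is open. Nor do the documents show that all primary claims outcomes are materially biased, or that OUD will rise at follow-up. No rates are given, sections 1, 3 and 9.1 list overdose rather than chronic use as the third outcome, and a workplace naloxone program matters here only if it leads to fills in members' pharmacy claims.

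**Conclusion.** The concern holds as a fault in outcome definition. As written, one fill matched by name or by the antidote class makes an OUD case with no supporting diagnosis. For Narcan this conflicts with the trial's own guidelines. For methadone and buprenorphine, workers with no other opioid are moved from possible overlap or chronic use into OUD. The two statements of the MAT rule also disagree.

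The size cannot be known from the documents. The range of 1.0% to 28.6% false among counted OUD cases covers the pain arm only and rests on assumed rates. It shows that the effect could be trivial or substantial. The error biases levels in any case, and biases the change between periods if fills of these drugs shift. It should be corrected before the claims outcomes are analysed, because the remedy needs no new data.

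**What to change.** 1. State one MAT rule and use it word for word in 9.4.2 and the appendix.
2. Replace the antidote and antagonist class with a list of named products that excludes naloxone rescue products.
3. Count a methadone or buprenorphine fill as MAT only if the product's indication category is not pain, or the member has an F11 code. Otherwise keep it in the opioid file, so that it can count toward overlap and chronic use.
4. State whether the same-day, different-provider arm of misuse is limited to opioid fills.
5. Report the baseline to follow-up change in OUD by diagnosis code alone as a sensitivity line beside the main outcome.

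The cost is a change of wording and one recode of fields already requested and already linked by patient identifier. The downside is that the indication field appears to describe the drug rather than the patient's reason for the fill. Some treated OUD patients without an F11 code may then be counted as opioid users, the reverse error. Report the number of ambiguous fills and show the claims outcomes under both codings.

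### As written, the overlap rule counts same-day opioid fills from one prescriber as misuse and leaves the different-provider arm of the misuse outcome with nothing to add

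*Combined protocol and SAP*

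**What the plan says.** Four definitions in the appendix on data management of administrative health claims matter here, together with section 9.4.2.

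- **Overlap (e.vi):** "Overlapping Rx: Date opioid fill is within previous days supply (current fill date < previous fill date + days supply". The only modifier covers a short course nested inside an earlier prescription, in which case "the prescription before the short course is used in evaluation". No exception is made for same-day fills, for the same prescriber or for early refills.
- **Same day, same prescriber (e.viii):** "Multiple Rx in a single visit: multiple Rx filled on the same day and NPI is the same between fills". This variable is not part of misuse.
- **Same day, different prescriber (e.ix):** "Multiple Rx on same day, different provider: multiple Rx filled on the same day and NPI between Rx different. Could indicate doctor shopping".
- **Misuse (e.x and section 9.4.2):** overlap, or "Multiple Rx on same day, different provider". Section 9.4.1 makes all three claims outcomes primary, and 9.4.2 lists misuse beside chronic use and opioid use disorder.

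A rule for same-day fills appears only under chronic use (e.vii.4): "When workers have multiple opioids filled on the same day, use the longest days supply in calculations". Nothing extends it to the overlap variable.

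**The concern.** The appendix treats same-day fills from one prescriber and same-day fills from different prescribers as different things. Only the second is linked to doctor shopping, and only the second is named in misuse. The overlap rule removes that distinction, because it looks at dates and days supply alone and a same-day fill always satisfies it.

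A worker given two opioid prescriptions at one visit would be reported as misusing opioids. Section 2.2 describes misuse as taking opioids other than as prescribed, and two same-day fills from one prescriber do not show that. The misuse proportion would then mix the behaviour the plan wants to measure with a prescribing pattern it set apart. Section 9.2 says these data will inform power calculations for a future trial, so the error would carry forward.

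**Working it through.** The plan states no misuse rate or sample-size figure to reproduce. The check is of the rule's logic.

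**Inputs.** Overlap inequality and short-course clause (e.vi), same-day variables (e.viii, e.ix), misuse composite (e.x and 9.4.2). Write d for the fill date and DS for days supply.

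1. *Two fills on one date.* Both dates equal d, so the test is d < d + DS. This is true for every DS of at least 1, whichever fill is taken as the previous one. With fills of 5 and 7 days supply on day 0, the test is 0 < 5 or 0 < 7, and both are true.
2. *Short-course clause.* It replaces the previous fill by an earlier one that runs out on the same day or later. The comparison date can only move later, so no same-day pair is exempted.
3. *Prescriber.* The prescriber identifier does not enter the inequality. Same-day, same-prescriber pairs are overlaps and therefore misuse. Same-day, different-prescriber pairs are also overlaps already, so the second arm is a subset of the first and the misuse count equals the overlap count.
4. *Enumeration.* Over every pair with days supply 1 to 90 by 1 to 90 (90 × 90 = 8,100), the rule flags 8,100 of 8,100 same-prescriber pairs and 8,100 of 8,100 different-prescriber pairs.
5. *Longer histories.* In 300,000 random histories of 2 to 6 fills with days supply of at least 1, 16,561 contained a same-day, different-prescriber pair and 0 of these were missed by the overlap rule. Of the 16,663 with a same-day, same-prescriber pair, 0 escaped it. These histories test the logic and do not estimate any rate.
6. *Exception.* If days supply of 0 is allowed, d < d + 0 is false. In a second set of 300,000 histories, 68 of 16,602 with a different-prescriber pair were then caught only by the second arm.
7. *After collapsing same-day fills.* The day-0 pair above becomes one dispensing with 7 days supply and no earlier fill, so it is not an overlap. With one prescriber it is not misuse. With two prescribers it is misuse through the second arm, which now has a function.
8. *Direction of the change.* With days supply of at least 1, every worker with a same-day pair is flagged under the present rule, and a worker without one is treated identically before and after. The corrected proportion therefore cannot be higher.

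Separately, a 30-day fill refilled on day 29 gives 29 < 30 and is flagged. On day 30 the test is 30 < 30, which is false. Collapsing same-day fills does not change this.

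**The case against.** The best reply is that *previous* in e.vi means a fill on an earlier date. The context supports this as the intention: same-day fills have their own variables, the appendix's descriptive list (g.v) tabulates overlap, both same-day variables and misuse on separate lines, and the OR in the misuse definition has a purpose only if overlap leaves same-day pairs out. The appendix also describes the variables as already generated, so the program may have handled this correctly. What stands is that the intention is fairly clear. The written rule still does not carry it out, and the one same-day instruction sits under a different variable. If the program already collapses same-day fills, the results are unaffected and the text needs a sentence.

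A second reply is that this is a feasibility study. Section 9.1 disclaims formal hypothesis testing, and section 3 defines success by recruitment and data collection. That limits the stakes, but misuse remains a primary outcome that 9.4.2 compares between periods. The separate counts in g.v help only in part, because they do not show how many workers are flagged solely through same-visit fills.

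A reader might infer more than the documents support:

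- *That every refill one day early is an error.* A zero-tolerance overlap is a clear and reproducible proxy, some early fills may reflect real misuse, and the documents give neither a tolerance nor a rate of early refills.
- *That the rule manufactures a fall from the three-year baseline to the one-year follow-up.* Unequal windows affect any ever-flag, including chronic use and opioid use disorder. Section 9.4.1 says the analysis will adjust for period length, although 9.4.2 names no method. That is a separate question, and this fix would not settle it.

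**Conclusion.** The rule is wrong as written. Given days supply of at least 1, it classes every same-day pair of opioid fills as misuse, against the plan's own separation of single-visit fills, and it makes the different-prescriber arm redundant. Missing or zero days supply would be an exception.

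The scope is the misuse outcome, one of three primary claims outcomes; chronic use and opioid use disorder do not use this rule. It covers opioid fills not classed as medication-assisted treatment, in members without a cancer diagnosis. Overlaps between different dates are still captured, so the documents do not support saying that the outcome fails to measure misuse at all. The extent of misclassification is unknown. It equals the number of workers whose only qualifying event is a same-day pair from one prescriber, and the study's own fill data can supply that count.

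**What to change.** In e.vi, state that same-day fills are first collapsed to one dispensing date with the longest days supply (the e.vii.4 convention), and that each dispensing is compared only with dispensings on earlier dates. Same-day fills then count as misuse only through the different-prescriber arm, which is evaluated on the uncollapsed fills. Repeat the rule in one sentence in section 9.4.2, apply it identically to baseline and follow-up, and say how missing or zero days supply is handled. If the program already does this, only the text changes.

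Optionally, because the strict inequality also flags a refill one day early, add a sensitivity version that ignores short overlaps, with the tolerance declared as an assumption.

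The cost is a few lines of code and a reported misuse proportion that is lower or unchanged. No new data are needed: fill date, days supply and prescriber identifier are already in the requested variable list.
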